**VERSION FINAL 4.0** CONFIDENTIAL **PAGE 5 OF 92** 

# PROTOCOL SYNOPSIS

Protocol Identifier	TH005						
Study Title	A Double-Blind, Randomised, Placebo-Controlled, Multi-Centre Field Study to Assess the Efficacy and Safety of HDM-SPIRE in Subjects with a History of House Dust Mite-Induced Rhinoconjunctivitis						
Protocol Version	FINAL 4.0						
Sponsor	Circassia Ltd						
Phase	II						
Indication	House dust mite (HDM)-induced rhinoconjunctivitis in subjects with clinically relevant symptoms.						
Objectives	
 
Primary Objective:
 
To evaluate the efficacy of HDM Synthetic Peptide Immuno-Regulatory Epitopes (HDM-SPIRE) in the reduction of symptoms and the use of allergy rescue medication associated with HDM allergy in subjects with clinically relevant symptoms.
 
Secondary Objectives:
 
To evaluate the safety and tolerability of HDM-SPIRE.
 
To evaluate the effect of HDM-SPIRE on rhinoconjunctivitis specific quality of life.
 
To evaluate the effect of HDM-SPIRE on sleep quality.
 
						
Study Design	The study will be a randomised, double-blind, placebo-controlled, parallel group, multi-centre field assessment of 3 dose regimens of HDM-SPIRE administered at 4 weekly intervals for 28 weeks.  Subjects will attend the investigative site for screening and administration of study medication and for periodic assessments of safety and efficacy. Subjects will also complete an electronic diary (eDiary) during four 3-week periods. These diaries will capture the primary efficacy variable data (symptom scores and medication use) as well as other patient reported data.						
Sample Size	A total of approximately 660 subjects will be randomised into the study, with approximately 165 subjects in each of the 3 HDM-SPIRE treatment groups and 165 in the placebo group. A 10% drop-out rate is assumed with the expectation that ~150 subjects per group will complete the study. Randomisation will be stratified according to severity of rhinoconjunctivitis symptoms at baseline and the presence of asthma.						
Study Population  Subjects aged 18-70 years with a documented history of moderate HDM-induced rhinoconjunctivitis (without asthma or with controlled Step 2 asthma according to the Global Initiative for Asthma (GINA) Guide							
Inclusion/Exclusion	Inclusion Criteria						
Criteria	
 
Male or female, aged 18-70 years.
 
A reliable history consistent with moderate to severe rhinoconjunctivitis (sneezing, rhinorrhoea, itchy nose, nasal blockage and/or itchy eyes, red eyes, watering eyes and/or itchy ear/palate) on exposure to HDM for at least 1 year and which has required symptomatic treatment on at least one occasion during the last year.
 
Mean Total Rhinoconjunctivitis Symptom Score (TRSS) ≥10 from 4 nasal symptoms and 4 non-nasal symptoms over a consecutive 7 day period before
 
						

**VERSION FINAL 4.0** CONFIDENTIAL **PAGE 6 OF 92** 

- the Screening Visit 1B/C.
- 4. Either Dermatophagoides pteronyssinus (Der p) or Dermatophagoides farinae (Der f) specific Immunoglobulin E (IgE) ≥0.35 kU/L measured by ImmunoCAP®.
- 5. Positive skin prick test (preferably using the ALK-Abello Allergen Extract test) to either Der p or Der f with a wheal diameter at least 5 mm (average of longest and orthogonal) larger than that produced by the negative control. The negative control must be <2 mm for the test to be valid.
- 6. Provide written informed consent.
- 7. Willing and able to comply with the study requirements.
- 8. If female and of childbearing potential, must practice a form of contraception with a failure rate of <1% when used correctly and produce a negative urine pregnancy test at the Screening Visit 1B/C.

### Additional Inclusion Criteria at end of the Baseline Evaluation (BAE) Period

- 9. Mean TRSS ≥12 from 4 nasal symptoms and 4 non-nasal symptoms during the BAE period (3 week period before randomisation).
- 10. Completed the eDiary during the BAE on at least 16 days (>75% of occasions)

#### **Exclusion Criteria**

- 1. Diagnosis of asthma requiring Global Initiative for Asthma (GINA) Step 3 (www.ginasthma.org)or higher treatment.
- 2. If asthmatic, experienced a deterioration of asthma that resulted in emergency treatment or hospitalisation in the 12 months before randomisation, or experienced a life-threatening asthma attack (e.g. one requiring intubation and mechanical ventilation) at any time in the past.
- 3. Used any oral or parenteral corticosteroid at any time within 1 month prior to Screening Visit 1B/C.
- 4. Asthma requiring high-dose inhaled corticosteroids (ICS) or anti-IgE therapy within 6 months prior to Screening Visit 1B/C.
- 5. Forced expiratory volume in 1 second (FEV1) <80% of predicted, or other evidence of partly controlled or uncontrolled asthma.
- 6. Clinically significant confounding symptoms of allergy to relevant local seasonal allergens (e.g. ragweed, mugwort, tree, grass or mould) and cannot complete the BAE and the final post-administration collection (PAC) period at 50-52 weeks (PAC3) outside the respective allergy seasons.
- 7. IgE ≥0.35 kU/L to other perennial allergens (e.g. animal dander, cockroach, mould) which cannot be avoided during the study or where sampling for these allergens demonstrates significant levels within the subject's home from dust and/or vacuum cleaner samples, analysed using Indoor biotechnologies Allergen Analysis Service.
- 8. Intends to be away for 7 days or more during the final PAC period at 50-52 weeks (PAC3), or whose lifestyle means that there is a high likelihood of them being away from home for more than 7 days during the PAC3 period.
- 9. Received an immunosuppressive treatment within 3 months prior to Visit 1B/C (except steroids for allergic and asthma symptoms).
- 10. Previous immunotherapy treatment with any HDM allergen product for more than 1 month within 5 years prior to screening.

CONFIDENTIAL **VERSION FINAL 4.0 PAGE 7 OF 92** 

- 11. Receiving ongoing treatment with any specific immunotherapy at screening.
- 12. Administration of epinephrine is contraindicated (e.g. subjects with acute or chronic symptomatic coronary heart disease or severe hypertension).
- 13. Use of beta-blockers, alpha-adrenoceptor blockers or monoamine oxidase inhibitors within 14 days before the Screening Visit 1B/C.
- 14. History of significant recurrent acute sinusitis, defined as 2 episodes per year for the last 2 years, all of which required antibiotic treatment, or a history of chronic sinusitis, defined as sinus symptoms lasting greater than 12 weeks that include 2 or more major factors or 1 major factor and 2 minor factors. Major factors are defined as facial pain or pressure, nasal obstruction or blockage, nasal discharge or purulence or discoloured postnasal discharge, purulence in nasal cavity, or impaired or loss of smell. Minor factors are defined as headache, fever, halitosis, fatigue, dental pain, cough, and ear pain, pressure, or fullness.
- 15. Females who are pregnant, lactating or planning to become pregnant, or donate ova for *in vitro* fertilisation during the study period or within 30 days following the study period. Female subjects unwilling to employ appropriate contraceptive measures to ensure that pregnancy will not occur either during or for 30 days following the completion of study period.
- 16. Significant history of alcohol or drug abuse.
- 17. Previously been treated in this or another HDM-SPIRE (ToleroMune-HDM) study.
- 18. Any history of severe drug allergy, severe angioedema or anaphylactic reaction.
- 19. Received treatment with an investigational drug within 30 days prior to the study.
- 20. Are unable to communicate or to understand the requirements of the study, or exhibit any psychiatric disorder, which would impair communication between the subject and the Investigator thereby interfering with the informed consent procedure or the gathering of study data.
- 21. History or findings on physical examination of any significant disease or disorder (e.g. cardiovascular, pulmonary, gastrointestinal, liver, renal, neurological, immunopathological, musculoskeletal, endocrine, metabolic, malignant, psychiatric, major physical impairment) which, in the opinion of the Investigator, may either put the subject at risk because of participation in the study, influence the results of the study or the subject's ability to participate in the study.
- 22. Dependent on the Investigator/site either for employment or education or are first degree relatives or partners of the Investigator/study staff.
- 23. Institutionalised because of a legal or regulatory order.
- 24. Active tuberculosis, auto-immune disorders, vaccination within 2 weeks before start of immunotherapy as well as subjects with hypersensitivity to excipients of HDM-SPIRE.

#### Additional Exclusion Criteria at end of BAE

25. Used any oral or parenteral corticosteroid during the BAE period.

# Investigational Product HDM-SPIRE Route of Administration Intradermal injection (100 μL)

VERSION FINAL 4.0 CONFIDENTIAL PAGE 8 OF 92

Treatment Regimen(s)	
 
8 x placebo 4 weeks apart
 
4 x 12 nmol HDM-SPIRE followed by 4 x placebo 4 weeks apart
 
4 x 12 nmol HDM-SPIRE 4 weeks apart followed by a second course of 4 x 12 nmol HDM-SPIRE 4 weeks apart
 
4 x 20 nmol HDM-SPIRE followed by 4 x placebo 4 weeks apart
 

Efficacy Parameters	
 
The following efficacy parameters will be measured in the study:
 
Combined Score [CS] (TRSS/8 plus Rescue Medication Score [RMS])
 
Rhinoconjunctivitis symptom scores (4 point categorical scale and visual analogue scale)
 
RMS
 
Nasal and non-nasal components of TRSS
 
Number of days subjects have no moderate or severe rhinoconjunctivitis symptoms score (RSS) symptoms without rescue medication usage
 
Rhinoconjunctivitis Quality of Life Questionnaire (RQLQ)
 
Asthma Control Test (ACT) in subjects with asthma
 
Home environment (exposure to allergen)
 
Pittsburgh Sleep Quality Index (PSQI)
 

	Clinical Global Impression of Change in Rhinoconjunctivitis Symptoms
Safety Parameters	
 
The safety and tolerability of HDM-SPIRE will be assessed by recording of:
 
Adverse Events (AEs)
 
Physical examination
 
Vital signs
 
Laboratory values (haematology, serum biochemistry, urine tests)
 
FEV1
 
Local reactions at the injection site
 

Pharmacokinetic	Local reactions at the injection site
Parameters	None
Statistical Analysis	A detailed Statistical Analysis Plan (including dictionaries for coding and software used) will be approved by the Sponsor prior to unblinding the study. If not otherwise specified, statistical significance is defined as p<0.05 and is 2-tailed when appropriate.  Data will be summarised with respect to demographic and baseline characteristics, efficacy variables and safety variables. Summary statistics will include the mean, N, standard deviation, median, minimum and maximum values for continuous variables and frequencies and percentages for categorical variables.  The primary efficacy variable will be the CS. This is derived from symptom scores and medication use recorded by subjects in an eDiary diary over a 3-week period on 4 occasions during the study. The primary endpoint for this study is the mean daily CS during the PAC3 period in HDM-SPIRE treated subjects compared with mean daily CS during the PAC3 in placebo treated subjects.  The primary analysis will be the comparison between the HDM-SPIRE treatment groups and placebo for the Intent-to-Treat (ITT) population using Mixed Model Repeated Measurement analysis for the PAC1, PAC2 and PAC3 mean CS assessments per subject. The model will include treatment, period and pooled centre as main effects, gender, asthma status and Baseline Allergy Evaluation CS as covariate and treatment by period interaction. An unstructured covariance matrix will be used to assess within-subject dependence of the 3 observations of mean CS.

**VERSION FINAL 4.0** CONFIDENTIAL **PAGE 9 OF 92** 

	difference in adjusted means between the active treatment groups and placebo will			
	be calculated, with the treatment contrast corresponding to the mean CS of the			
	PAC3 period. A hierarchical (step-down) approach will be used to control the			
	overall type 1 error rate at 5%.			
	Other endpoints will be analysed appropriately. Supportive analysis will include			
	non-parametric methods, as appropriate.			
Safety data will be analysed descriptively. The primary safety endpoint will be				
	comparison of the number of adverse events, and subjects with adverse events, in			
	the HDM-SPIRE groups compared to placebo.			
Study Sites	To be determined.			
Planned Study Dates				
Start of clinical phase	Q4 2014			
End of clinical phase	Q4 2016			
Duration of the Study	The duration of the study for each subject will be approximately 62 weeks.			

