# 7.5.4 Safety Analysis

Safety will be evaluated by analysis of the following parameters:

- AEs;
- Physical examination;
- Clinical laboratory tests (including immunology);
- FEV1;
- Vital signs;
- Local reactions at the injection site.

The primary safety endpoint will be a comparison of the number of adverse events, and subjects with adverse events, in the HDM-SPIRE groups compared to placebo.

For safety analysis, descriptive statistics such as N, mean, median, minimum, maximum and SD will be summarised by treatment group for continuous variables. Frequency distribution will be summarised for categorical variables. No formal inferential tests will be performed on safety data.

The number and percentage of subjects who experience AEs will be presented by treatment group. Based on the MedDRA Preferred Term, subjects who experience the same AE on multiple occasions will be summarised at the maximum severity and most conservative relationship to the study medication. If 2 or more AEs are reported as a single event, the

VERSION FINAL4.0 CONFIDENTIAL PAGE 74 OF 92

individual terms will be reported as separate AEs.

The total number of AEs will be summarised by MedDRA System Organ Class and Preferred Term for each treatment group. Descriptive statistics will be presented for differences between the HDM-SPIRE treatment groups and the placebo group, but no hypothesis testing is planned.

Any deaths, SAEs and AEs leading to discontinuation of study medication administration will also be summarised by treatment group.

Local reactions at the injection site will be summarised by type of reaction and visit for each treatment group.

Physical examinations data will be listed only.

Vital signs will be presented as descriptive statistics on absolute values and the change from baseline will be summarised for each treatment group by visit.

 $FEV_1$  will be presented as descriptive statistics and the absolute change from baseline and percentage change from baseline will be summarised for each treatment group by visit.

Clinical laboratory data for individual subjects will be listed and any out of range values will be highlighted. Laboratory data will be summarised for each treatment group by visit as follows: summary of absolute values and change from baseline and analysis of shifts from baseline.

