## 16. SAFETY OUTCOMES

All outputs for safety outcomes are to be based on the SAF population.

There is to be no statistical comparisons between the treatment groups for safety data, unless otherwise specified within the relevant section.

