### 16.1. ADVERSE EVENTS

An AE is defined as any untoward medical occurrence in a subject administered study treatment that does not necessarily have a causal relationship with the treatment. An AE can therefore be any unfavourable and unintended sign (i.e. an abnormal laboratory finding), symptom (i.e., rash, pain, discomfort, fever, dizziness, etc.), disease (i.e., peritonitis, bacteraemia, etc.) or outcome of death temporally associated with the use of study treatment, whether or not considered causally related to the study medication.

Adverse Events (AEs) are to be coded using MedDRA Version 19.0.

Adverse events are to be classified as either pre-treatment AEs or treatment-emergent adverse events (TEAEs) based on the start date of the event as follows:

- Pre-treatment AEs: Defined as any AE which started or worsened on or after informed consent and before study medication administration
- TEAE: Defined as any AE which started or worsened on or after first study medication administration.

See Appendix 2 for handling of partial dates for AEs. In the case where it is not possible to define an AE as treatment-emergent or not, the AE is to be classified as the worst case; i.e. treatment-emergent.

An overview of the frequency (n) and percentage (%) of subjects is to be provided for the following TEAEs together with the actual number of mentions (m) of the event per category:

- Any TEAE
- Serious TEAEs
- TEAEs leading to death

---

Document: TH005 SAP Version 2.docx

Author: [name]

Version Number:

2.0

Version Date:

24MAR2017

Template No: CS\_TP\_BS016 – Revision 3

Effective Date: 01May2012

Reference: CS\_WI\_BS005

Copyright © 2012 Quintiles Transnational Corp. All rights reserved.

The contents of this document are confidential and proprietary to Quintiles Transnational Corp. Unauthorized use, disclosure or reproduction is strictly prohibited.

---

- Life-threatening TEAEs
- TEAEs leading to premature study and treatment discontinuation
- Treatment related TEAEs leading to premature treatment discontinuation
- Severe TEAEs
- TEAEs related to study medication
- TEAEs of special interest
- TEAEs within 24 hours of any dose of study medication

In addition to the overview of TEAEs, incidence of all TEAEs in the sub-sections below is to be presented by System Organ Class (SOC) and Preferred Term (PT). If an AE occurs more than once the subject is to be counted once per SOC and PT as relevant.

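### SAP 16.1 does not name the protocol's primary safety endpoint and omits the promised descriptive differences from placebo; its per-arm summaries also take no account of follow-up time

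*Protocol*

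**What the plan says.** The Protocol Synopsis and Protocol 7.5.4 define the same endpoint. The Synopsis words it as a "comparison of the number of adverse events, and subjects with adverse events, in" each active arm relative to placebo. The protocol makes the analysis descriptive. The Synopsis says "Safety data will be analysed descriptively", and 7.5.4 says "No formal inferential tests will be performed on safety data". It still commits to showing the contrast with placebo: "Descriptive statistics will be presented for differences between the HDM-SPIRE treatment groups and the placebo group, but no hypothesis testing is planned".

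SAP 16 states "There is to be no statistical comparisons between the treatment groups for safety data", with an exception where a section specifies otherwise. None of the AE sections (16.1 to 16.1.8) does so. SAP 16.1 asks for the number and percentage of subjects in each TEAE category, "together with the actual number of mentions (m) of the event per category". It names no primary safety endpoint and gives no active-placebo difference, interval or person-time.

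On follow-up:
- Protocol 6.4.1 collects AEs from consent to Visit 5.
- Protocol 6.2.2.2 sends subjects withdrawn from the study before the final dose straight to Visit 5.
- SAP 5.4 keeps them in the Safety population if they had one dose and one post-baseline safety assessment.
- SAP 13.1 defines exposure as first to last dose. That is not AE follow-up time and is not linked to the AE tables.

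**The concern.** The one safety endpoint that the protocol calls primary is a contrast with placebo. The SAP text supplies its ingredients by arm but not the contrast, and does not say why the promised differences were dropped.

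This matters in a dose-selection trial. Protocol 2.0 says the study is to identify a dose and regimen for Phase 3. Protocol 1.3.1 says the safety and tolerability of unit doses above 12 nmol are unknown, and gives equivalent safety and tolerability as part of the rationale for the 4 x 20 nmol arm. Percentages side by side, without an interval, do not show how large an excess over placebo the data can exclude.

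Follow-up time is a second gap. Withdrawal from the study can be linked to tolerability: AEs are a listed reason in Protocol 4.6, and poor tolerance of two consecutive half doses is one in 5.5.1. Such subjects leave AE observation early but stay in the denominator.

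**Working it through.** **Plan's own figures.** The documents give no AE rate, target safety difference or safety precision, so there is no plan figure to reproduce. The usable inputs are about 165 subjects per arm (Protocol 4.1), AE collection to about week 52 (6.4.1 with 3.1), dosing from week 0 to week 28 (Table 2), and 10% drop-out overall with no figure per arm (4.1, 7.2). Withdrawal rates by arm, their timing and the AE rates below are assumptions.

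**Raw mentions.** Let the true AE rate be equal in two arms. Let d be the proportion withdrawn and f the mean fraction of the at-risk period that a withdrawn subject loses. Expected mentions are proportional to 1 − d·f, so the ratio of mentions is (1 − d₁f)/(1 − d₀f).

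| Assumed pattern | f | Ratio | Shortfall |
|---|---|---|---|
| 20% v 5%, even over 52 weeks, AEs throughout | 0.5 | 0.900/0.975 = 0.923 | 7.7% |
| 20% v 5%, even over 52 weeks, AEs only in weeks 0–28 | 0.269 | 0.946/0.987 = 0.959 | 4.1% |
| 20% v 5%, all at week 6, AEs throughout | 46/52 = 0.885 | 0.823/0.956 = 0.861 | 13.9% |
| 20% v 10%, even, AEs throughout | 0.5 | 0.900/0.950 = 0.947 | 5.3% |
| 20% v 10%, all at week 4, AEs throughout | 48/52 = 0.923 | 0.815/0.908 = 0.898 | 10.2% |
| Equal withdrawal, same timing | any | 1 | 0 |

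In row 2, a subject withdrawing at a uniform time over 52 weeks is observed for 28 − 28²/(2 × 52) = 20.46 of the 28 weeks, so f = 1 − 20.46/28 = 0.269.

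Read the other way, with 20% v 10% spread evenly, a true rate excess of 1/0.947 − 1 = 5.6% in the higher-withdrawal arm would appear as equal raw counts.

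**Percentage of subjects.** This also ignores follow-up. Take a constant 1 AE per person-year and even withdrawal. A completer has probability 1 − e⁻¹ = 0.632 of at least one AE, and a withdrawn subject averages 0.368.
- 20% withdrawn: 0.8 × 0.632 + 0.2 × 0.368 = 57.9%.
- 10% withdrawn: 0.9 × 0.632 + 0.1 × 0.368 = 60.6%.

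The gap is about 2.6 points before rounding, with no true difference in rate.

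**Precision of the missing contrast.** With 165 per arm and the same incidence p in both arms, the 95% half-width is 1.96·√(2p(1 − p)/165).
- p = 0.5: 1.96 × 0.0550 = 10.8 points.
- p = 0.1: 1.96 × 0.0330 = 6.5 points.

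Percentages that look alike would therefore be compatible with sizeable differences in either direction.

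**Practice elsewhere in the SAP.** SAP 15.3.1.2 (PSQI good response) and 15.3.1.4 (concomitant allergy medication, Safety population) both specify a difference in proportions from placebo with an exact 95% CI. Two exploratory endpoints receive the summary that the primary safety endpoint lacks.

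**The case against.** The case for leaving the SAP alone has real content.

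- **No conflict on testing.** A reader might infer that the SAP forbids comparing arms. It bars only statistical comparisons, with an exception clause, and the protocol also rules out inferential tests. The gap is the descriptive difference, not a test.
- **Both components are tabulated.** A reader might infer that only raw counts are given, or that the endpoint cannot be obtained. SAP 16.1 gives percentages as well as mentions for every arm, so the point difference is one subtraction. The output templates cited in SAP 8 are not among the documents and might show it.
- **No rate or interval was promised.** The protocol speaks of numbers of events and subjects. Person-time and intervals are improvements, not overdue commitments. This stands.
- **The direction is not fixed.** A reader might infer that an arm with more drop-outs must show fewer events. That requires similar AE rates and real loss of follow-up. Withdrawal caused by AEs could go with more events, and the triggering event is itself counted. Placebo could lose more subjects through lack of response. Protocol 4.6 also says that stopping treatment need not mean leaving the study.
- **Imbalance is visible elsewhere.** Disposition with reasons (SAP 9), exposure (13), TEAEs leading to discontinuation (16.1.5, 16.1.6) and the independent DSMC (Protocol 10.0) would all help to reveal it. This limits the harm, but none of these SAP summaries is specified as an AE comparison on a common time base.

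These arguments narrow the point. They do not supply the difference that Protocol 7.5.4 promises.

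**Conclusion.** The point holds as an inconsistency between protocol and SAP, with a modest analytic weakness attached. The SAP text neither names the primary safety endpoint nor specifies the descriptive active-placebo differences that the protocol commits to. This rests on the text alone.

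The follow-up effect is conditional. If underlying AE rates are similar and one arm loses more subjects from the study, or loses them earlier, mentions and percentages can be too low in that arm. For 20% v 5% withdrawal, mentions fall by about 4% to 8% when withdrawal is even, depending on whether AEs are confined to the dosing period or run to week 52, and by up to about 14% when it clusters around week 6. There is no distortion if withdrawal is balanced. Those withdrawal rates are illustrative; the documents give only 10% overall.

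This does not threaten the validity of the trial. It is a cheap improvement that lets the trial report the comparison it calls primary.

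**What to change.** In SAP 16.1, name the primary safety endpoint as the protocol defines it and add one table giving, for each HDM-SPIRE arm against placebo:

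1. The difference in percentage of subjects with at least one TEAE, with a descriptive 95% CI.
2. Raw mentions and, beside them, TEAEs per subject-year, counting time from first dose to the last AE-collection date, with a descriptive difference or ratio whose 95% CI allows for repeat events within a subject. A negative binomial model with log follow-up time as offset would serve, but that choice is optional.

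Give no p-values. Reword the SAP 16 sentence so that it rules out hypothesis tests rather than statistical comparisons, in line with Protocol 7.5.4.

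The cost is one SAP paragraph, one extra table and a small amount of programming, all from data already collected.
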